7.0 Data and Specimen Banking*

N/A

8.0 Sharing of Results with Subjects*

8.1 Results will not be shared with subjects.

9.0 Study Timelines*

- 9.1 An individual study subject's participation in the study should last 2-10 hours depending on the duration of the surgical procedure.
- 9.2 All study subjects should be enrolled within 1 year of the start of the study.
- 9.3 The study data will be analyzed, a manuscript written, and the study completed within 18 months of the start of the study.

10.0 Inclusion and Exclusion Criteria*

- 10.1 Potential subjects will be identified by reviewing the surgery schedule in Epic and will be recruited from the main OR pre-operative area the day of their surgery.
- 10.2 Inclusion criteria: ASA 1-4 patients, weighing 10 to 80 kg undergoing a surgical procedure with general anesthesia and requiring an invasive arterial cannula.
- 10.3 Exclusion criteria:
 - Patients with history of a peripheral neurologic or neuropathic disorder
 - Patients in whom the upper extremity cannot be used for blood pressure monitoring
 - Patients in whom an invasive arterial cannula cannot be placed
 - Patients with vascular implants at the sites of non-invasive blood pressure measurement (fingers and upper arm of the examined arm)
 - Edematous patients

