1.0 Study Summary

Study Title	Accuracy of the NICCI™ monitor in providing beat-to-beat non-invasive blood pressure readings in children and adolescents
Study Design	Prospective, non-blinded comparative study
Primary Objective	The primary objective of this study is to compare the blood pressure reading (systolic, diastolic, and mean) from an arterial cannula with the readings obtained from the non-invasive continuous blood pressure monitoring, NICCI™
Secondary Objective(s)	None
Research Intervention(s)/ Investigational Agent(s)	Measuring beat-to-beat blood pressure non-invasively with the NICCI™ monitor. There will be no change in anesthetic management or use of investigational pharmacological agents.
IND/IDE #	Not applicable
Study population	Patients who are scheduled for elective, urgent or emergent surgery
Sample size	150 (50 in each of 3 weight groups 10-20 kg, 20-40, and \geq 40 kg)
Study duration for individual participants	Duration of the surgical procedure (2-10 hours)
Study Specific Abbreviations/ Definitions	BP = blood pressure sBP = systolic blood pressure dBP = diastolic blood pressure MAP = mean arterial pressure NIBP = non-invasive blood pressure IBP = intra-arterial blood pressure

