3.2 The NICCI, Pulsion/GETINGE uses novel technology to provide a continuous estimation of BP displayed as a waveform similar to that seen with an invasive arterial cannula (information attached). Infrared (IR) light, emitted from a Light Emitting Diode, is sent through the finger. The light is partly absorbed by the arterial blood, which is changing according to the heart activity (pulse). A light detector receives the remaining light on the other side of the finger and thus detects the continuous pulse signal. Counter pressure is exerted from the outside in such a way that the arterial wall is totally unloaded. This continuously changing outside pressure keeps the arterial blood volume constant at all times and directly corresponds to the arterial pressure. The intra-arterial pressure is therefore measured indirectly. To calibrate the continuous pulse-contour curve with the correct absolute blood pressure values, an automatic non-invasive blood pressure (NIBP) measurement is either performed on the patient's upper arm or provided by the user. This device is based on technology originally developed as the CNAP™ monitor which has been tested and validated by us previously in other IRB-approved trials.

23 Tobias JD, McKee, Herz D, Teich S, Sohner P, Rice J, Barry N, Michalsky M. Accuracy of the CNAP™ monitor, a non-invasive continuous blood pressure device, in providing beat-to-beat blood pressure measurements during bariatric surgery in severely obese adolescents and young adults. *J Anesth* 2014;28:861-865.

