6.0 Procedures Involved*

6.1 This is a prospective study that will compare the blood pressure readings from an arterial cannula with those obtained non-invasively by the NICCI device. The study will enroll 50 patients into each of three weight ranges: 10-20 kg, 20-40 kg, and 40-80 kg.

6.2 The study cohort will include patients requiring anesthetic care and in whom an indwelling arterial cannula will be placed for the surgical procedure. The arterial cannula will not be placed for the purpose of the study. The NICCI™ monitor will be attached to the patient and simultaneous readings from the NICCI™ monitor and the invasive arterial cannula will be downloaded every minute into a laptop computer for later analysis.

6.3 Exclusion criteria:

- Patients with history of a peripheral neurologic or neuropathic disorder
- Patients in whom the upper extremity cannot be used for blood pressure monitoring
- Patients in whom an invasive arterial cannula cannot be placed
- Patients with vascular implants at the sites of non-invasive blood pressure measurement (fingers and upper arm of the examined arm)
- Edematous patients

6.4 There are no foreseeable risks associated with the use of NICCI™ device.

6.5 The data (BP readings) will be downloaded into a bedside NCH laptop in the operating room and stored on our password-secured server.

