11.0 Vulnerable Populations*

- 11.1 We will include children, and will not include adults, pregnant woman, and prisoners as they are not part of our usual patient population.

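### Do the missing age limit in 10.2 and the shared weight-band end points leave the study population or its groups undefined?

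*Combined protocol and SAP*

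**What the plan says.** **Eligibility.** Section 10.2 includes "ASA 1-4 patients, weighing 10 to 80 kg undergoing a surgical procedure with general anesthesia and requiring an invasive arterial cannula". The exclusion lists in 6.3 and 10.3 do not mention age, and the Study Summary describes the population only as "Patients who are scheduled for elective, urgent or emergent surgery".

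**Age.** Section 11.1 states: "We will include children, and will not include adults, pregnant woman, and prisoners as they are not part of our usual patient population". The study title refers to "non-invasive blood pressure readings in children and adolescents". Sections 13.1 and 22.2 describe consent from a parent or guardian with assent from the patient. No section gives the age at which a patient counts as an adult.

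**Weight bands.** The Study Summary plans "50 in each of 3 weight groups 10-20 kg, 20-40, and" at least 40 kg. Section 6.1 enrols 50 patients into each of "three weight ranges: 10-20 kg, 20-40 kg, and 40-80 kg". Section 12.1 repeats 150 in total with 50 per weight range. Section 17.1 plans a Bland-Altman analysis for three groups without defining them again. The weight bands are the natural reading.

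**The concern.** Staff screen patients against the inclusion and exclusion criteria. If those carry no age limit, an adult of 40 to 80 kg meets every listed item, and each one enrolled would be 1/50 = 2% of the patients in the top band of a pediatric accuracy study. Section 11.1 rests on adults not being usual patients, yet section 3.2 cites previous work with the predecessor device "in severely obese adolescents and young adults".

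The bands are both enrolment quotas and, apparently, analysis groups. With shared end points, a child of exactly 20 or 40 kg fits two of them. In a non-blinded study whose data go to the manufacturer for a regulatory submission (17.2), any freedom over group membership deserves a look. Finally, a 90 kg patient fits the Summary's top band but not the one in 6.1.

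**Working it through.** **1. Sample size.** Three bands (Study Summary, 6.1) at 50 patients each: 3 × 50 = 150. This matches the stated total and does not depend on how the boundaries are closed.

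**2. Which bands each weight fits**, with both ends of every range inclusive as printed:

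| Weight (kg) | Study Summary | Section 6.1 | Eligible under 10.2 |
|---|---|---|---|
| 10, 15 | first | first | yes |
| 20 | first and second | first and second | yes |
| 30 | second | second | yes |
| 40 | second and third | second and third | yes |
| 60, 80 | third | third | yes |
| 90 | third | none | no |

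The two band lists disagree only above 80 kg, where 10.2 has already excluded the patient. Among eligible weights, only exactly 20 and exactly 40 kg are ambiguous.

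**3. How many children sit on a boundary.** The documents give neither a weight distribution nor a recording precision, so both are assumed. With weights spread evenly within a band:

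- Recorded to 1 kg, first band: 11 values, 1 shared. 1/11 = 9.1%, and 0.091 × 50 = 4.5 children.
- Recorded to 1 kg, second band: 21 values, 2 shared. 2/21 = 9.5%, and 0.095 × 50 = 4.8 children.
- Recorded to 0.1 kg: 1/101 and 2/201, each about 1%, or 0.5 of 50.

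These are upper bounds. A 20 kg child is counted in both lower bands, so the figures must not be added. If weights were instead even over the whole 10–80 kg range, the ambiguous share would be 2/71 = 2.8% of all patients (0.028 × 150 = 4.2) at 1 kg precision, or 2/701 = 0.3% (0.4 of 150) at 0.1 kg.

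**4. What a boundary decision could do to a band's mean difference.** Suppose boundary children make up a share p of a band, each child counts equally, and their mean difference between devices departs from the rest of the band by d. Including them rather than leaving them out moves the band mean by p × d. The documents give no d. As an illustration only, take d = 5 mmHg, the closeness threshold used in 17.1. The shift is then 0.091 × 5 = 0.45 mmHg (first band) or 0.095 × 5 = 0.48 mmHg (second band) at 1 kg precision, and about 0.01 × 5 = 0.05 mmHg at 0.1 kg. That requires every boundary child to be moved the same way.

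**5. Adults, sections side by side.** Section 10.2 is silent on age. Section 11.1 states that the study "will not include adults", and the title agrees. The consent sections provide no route for an adult consenting alone. Silence in one section against an express statement in another is not a contradiction, and the express statement governs.

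**6. When the band is fixed.** Section 6.1 enrols patients into weight ranges, consent is taken before surgery (13.1, 22.1), and readings begin in the operating room (24.0). The natural order is weight, band, then readings.

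**The case for a change.** The best case for a change is that 11.1 is a statement about vulnerable populations, not a screening criterion, and that its stated reason is usual practice. The cited study of young adults suggests such patients do reach this team, and the protocol never says at what age adulthood starts. A pre-specified boundary rule would cost a few words and remove any doubt in a data set meant for a regulator.

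Some of this stands. The cut-off age is not written down, and no rule places a child of exactly 20 or 40 kg. The rest is weaker. The title of an earlier study of another monitor, in bariatric surgery, does not show who will be enrolled here and cannot override 11.1. The documents give no expected number of adults, so 2% per adult is a unit, not an estimate. Choosing a band after seeing readings would require departing from the order in 6.1 and could involve only exact-boundary children. Filling whichever quota is still open is possible for those children, but it depends on enrolment counts and not on how well the two devices agree.

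**Conclusion.** No change follows. The age point is a restriction stated in 11.1 and the title but not repeated in 10.2, and staff following the whole protocol would apply it. The open-ended top band is a clerical shortening in the Summary with no effect once the 80 kg cap is applied. The shared end points are a small gap that an analyst fills by closing each band at one end. A child at a boundary weight represents either neighbouring band about equally well.

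The size is bounded at roughly 0.5 to 4.8 of 50 children in either lower band. This assumes evenly spread weights and recording to 0.1 or 1 kg, neither of which the documents state. The total of 150, the method of analysis and the intended population are unaffected, and no effect on bias or limits of agreement has been demonstrated. The conclusion also rests on reading enrolment into a weight range as preceding the first reading, which the order of procedures supports.

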11.0 Vulnerable Populations*

- 11.1 We will include children, and will not include adults, pregnant woman, and prisoners as they are not part of our usual patient population.

12.0 Local Number of Subjects

- 12.1 150 (50 in each weight range of routine, urgent, and emergent cases).

13.0 Recruitment Methods

- 13.1 Potential subjects will be recruited in the surgical preoperative area on the day of the surgery. The research team will contact the guardian/parents and obtain consent. Assent will also be obtained from age appropriate patients.
- 13.2 The patients to be recruited are those who are scheduled for surgery under general anesthesia in the NCH operating rooms.
- 13.3 Using Epic, the research team will check the patients scheduled for planned surgery in the NCH operating rooms.

14.0 Withdrawal of Subjects*

Patients may withdraw from the study at any time.

15.0 Risks to Subjects*

15.1 Although not likely, there may be a potential risk for breach of patient health information. There is no study related physical risk to study subjects associated with this study. All study related procedures are non-invasive.

15.2 Subject information will not be given to any other investigators. Subjects and their information will be closely monitored and guarded by study staff; there will be limited access to patients and their information by trained study staff; and subject information will only be shared and discussed between study staff specific to this study. Subject PHI will be stored in a locked cabinet, and will be stored and maintained in password protected computer files.

16.0 Potential Benefits to Subjects*

16.1 There are no specific immediate benefits to the patient.

17.0 Data Management* and Confidentiality

17.1 Statistical analysis and data presentation will include a calculation of the absolute difference of the sBP, dBP and MAP values of the two devices. To avoid biasing the data, the absolute not directional difference will be used. For example, if the reading from NICCI™ device was 10 mmHg above or below the reading from the AL, a value of 10 mmHg was used, not -10 or +10 mmHg. Additionally, a determination will be made of the percentage of values from the NICCI™ device that are \leq 5 mmHg and more than 10 mmHg from the IBP values. A Pearson correlation coefficient will be calculated comparing the sBP, dBP and MAP values between the arterial cannula and the NICCI™ device. A Bland-Altman analysis with multiple measurements per subject will be performed to determine the bias and 95% level of agreement for the three groups.

17.2 De-identified data will be shared with the manufacturer of the monitor, Getinge. They will be assisting with data analysis, as well as, using the data for a 510(K) submission to the FDA.

17.3 Research records will be stored in a locked cabinet and password protected computer. Only certified research personnel will be given access to identifiable subject information

17.4 Following publication of study results, research records will be stored for a period of 5 years and then will be destroyed by placing in a secure shredding bin.

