2.0 Objectives

2.1 The primary objective of this study is to compare blood pressure (BP) readings obtained from an invasive arterial cannula and a non-invasive continuous BP device. The hypothesis is that this novel non-invasive device will provide an accurate and continuous estimation of BP.

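### Does the absolute-difference rule in section 17.1 undermine the Bland-Altman bias and limits of agreement?

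*Combined protocol and SAP*

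**What the plan says.** The analysis text is one paragraph, section 17.1 (under 17.0 Data Management and Confidentiality). In order, it lists:

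1. A summary of error size: "Statistical analysis and data presentation will include a calculation of the absolute difference of the sBP, dBP and MAP values of the two devices". The next sentence gives the reason, "To avoid biasing the data, the absolute not directional difference will be used", and an example follows in which a reading 10 mmHg above or below the arterial line is treated alike: "a value of 10 mmHg was used, not -10 or +10 mmHg".
2. In a sentence opening with *Additionally*, threshold percentages: "a determination will be made of the percentage of values from the NICCI™ device" that lie within 5 mmHg, or more than 10 mmHg away, from the arterial values.
3. A Pearson correlation for each of the three pressures.
4. An agreement analysis: "A Bland-Altman analysis with multiple measurements per subject will be performed to determine the bias and 95% level of agreement for the three groups".

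No sentence gives the order of subtraction for item 4 or says in words that its differences are signed. Section 6.2 says the simultaneous readings from both devices "will be downloaded every minute into a laptop computer for later analysis". Section 17.2 says of the manufacturer: "They will be assisting with data analysis, as well as, using the data for a 510(K) submission to the FDA".

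**The concern.** The study has one objective, and section 2.1 states its hypothesis as "this novel non-invasive device will provide an accurate and continuous estimation of BP". Whether the device tends to read high or low is part of accuracy. Of the four listed analyses, the mean absolute difference, the threshold percentages and the Pearson coefficient cannot show direction. Only Bland-Altman can, and only with signed differences. The sentence on absolute differences carries no explicit limit to one summary, so it could be taken as a rule for the whole paragraph.

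The reason given is also poor. Removing the sign does not avoid bias in the Bland-Altman sense; it hides a systematic offset. Because the manufacturer will help with the analysis and use the data in a regulatory submission, more than one party may work from this text. If someone applied the absolute rule to the Bland-Altman step, the reported bias could never be negative and the limits would be too narrow.

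**Working it through.** The plan gives no expected bias, SD or acceptance margin, so it has no figure to reproduce. The check has two parts: how the paragraph reads, and what a misreading would cost.

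**How the paragraph reads**

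- The first sentence says the analysis will *include* the absolute difference, which makes it one item among several. The sentence on direction and the 10 mmHg example come straight after it and explain that item.
- *Additionally* then opens a new item. The correlation and the Bland-Altman analysis follow in their own sentences, each with its own output.
- The Bland-Altman sentence names its output as the bias and the 95% agreement range. Both are defined on signed differences, so the method and its output fix the input.
- The plan's example shows why both summaries are useful. For one reading 10 mmHg high and one 10 mmHg low, the signed mean is (10 − 10)/2 = 0 and the absolute mean is (10 + 10)/2 = 10. The first shows no net offset; the second shows the typical size of error. On this reading, the stated reason is a loose way of saying that opposite errors should not cancel.

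**What each summary can show**

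Assume normal differences d with mean μ (the bias) and SD σ. The values of μ and σ below are assumptions. For absolute differences:

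- E|d| = σ√(2/π)·exp(−μ²/2σ²) + μ[1 − 2Φ(−μ/σ)]
- SD|d| = √(μ² + σ² − E|d|²)

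Take σ = 8. Devices with μ = +5 and μ = −5 give the same sign-free results:

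- E|d| = 7.6 mmHg
- 39% of readings within 5 mmHg
- 30% of readings more than 10 mmHg away
- the same Pearson coefficient, which a constant offset does not alter

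Signed limits, μ ± 1.96σ, separate the two devices: −10.7 to 20.7 for μ = +5, and −20.7 to 10.7 for μ = −5. The plan includes this analysis, so direction is not lost.

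**What a misreading would cost**

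This applies only if |d| replaced d in the Bland-Altman step. The limits would then be E|d| ± 1.96·SD|d|, and their width would shrink by 1 − SD|d|/σ.

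| True bias (mmHg) | SD (mmHg) | Signed limits | Reported bias from absolute values | Limits from absolute values | Narrowing |
|---|---|---|---|---|---|
| 0 | 5 | −9.8 to 9.8 | 4.0 | −1.9 to 9.9 | 40% |
| 0 | 8 | −15.7 to 15.7 | 6.4 | −3.1 to 15.8 | 40% |
| 0 | 12 | −23.5 to 23.5 | 9.6 | −4.6 to 23.8 | 40% |
| +5 | 8 | −10.7 to 20.7 | 7.6 | −3.4 to 18.6 | 30% |
| −5 | 8 | −20.7 to 10.7 | 7.6 | −3.4 to 18.6 | 30% |

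For the last two rows, 1 − 5.60/8 = 0.30. With a bias of +5 or −5 and an SD from 5 to 12, the narrowing runs from 20% to 35%. A simulation of 50 subjects with 120 readings each (2 hours at one per minute), total SD 10 and variance-components limits gave 40% at zero bias and 33% at ±5, so repeated measurement does not remove the effect.

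The mistake would be easy to see. No plotted difference would fall below zero, yet every lower limit in the table is negative, a value an absolute difference cannot take.

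**The case for a change.** The strongest case for amending the text is that it never says the Bland-Altman differences are signed. This paragraph is the only analysis text, its reason for dropping the sign is wrong if bias means systematic offset, and the manufacturer will also take part in the analysis. One or two sentences would settle the matter without new data. Even on the natural reading, the order of subtraction is not fixed in advance.

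Some of this stands. The order of subtraction is unstated and the reason is badly phrased. But reversing the order only mirrors the result: a bias of +5 with limits −10.7 to 20.7 becomes −5 with limits 10.7 down to −20.7. That is a matter of labelling the axis when results are reported. Deleting the poor reason would leave every computed quantity as it is. Nor does the plan put the absolute difference in place of the signed analysis, since it lists both. Section 17.2 says the manufacturer will assist; it does not suggest that the parties will work separately from conflicting readings of 17.1.

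**Conclusion.** No change follows. An analyst following section 17.1 would report a mean absolute difference as a summary of error size and, beside it, a signed Bland-Altman bias with repeated-measures limits for each weight group. These are compatible. The narrowing of about 40% at zero bias, or 20% to 35% at an assumed bias of ±5 mmHg, belongs to a hypothetical mistake that no sentence in the plan instructs. The size of the problem in the plan as written is therefore nil for the computed results; what is left is a sign label and a loosely worded reason.

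This conclusion rests on two things: that Bland-Altman is done in its standard form, which naming the method and its bias output implies, and that the paired one-minute readings are stored as section 6.2 describes, so that signed differences can always be computed. The numerical illustrations also assume normal differences and SDs of 5 to 12 mmHg, none of which the documents state.

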3.0 Background

3.1 BP is one of the most important parameters in several clinical settings. Particularly during the perioperative period, BP needs to be monitored repeatedly or even continuously to facilitate the best care for patients. This is done either intermittently using an oscillometric non-invasive blood pressure device (NIBP) or continuously by an invasive arterial line (IBP). A number of clinical studies show that both methods may have pitfalls and at times be inaccurate. Since the NIBP provides discontinuous pressure readings with the current recommendations for intraoperative monitoring stating that the BP should be monitored every 5 minutes, hemodynamic events may be missed or there may be a delay in recognition of alterations in BP. Therefore, during major intraoperative procedures in patients with co-morbid cardiac diseases or during procedures with significant blood loss, invasive arterial monitoring of BP is chosen with placement of an intra-arterial cannula. Although generally safe and effective, the placement of an intra-arterial cannula may be

PROTOCOL TITLE: Accuracy of the NICCI™ monitor

associated with complications including artery occlusion with distal ischemia, hematoma formation, blood loss due to unintended disconnection, infection or nerve damage with sensory disturbance. More importantly, arterial cannulation takes time and may at times be impossible. Therefore, a method that non-invasively allows the continuous measurement of BP would be clinically useful.

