4.0 Study Endpoints

4.1 The primary study endpoint is to compare the BP readings from the non-invasive NICCI device with those obtained from an arterial cannula.

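### The Pearson correlation in section 17.1 makes no allowance for repeated readings; if pooled over one-minute pairs, it shows neither agreement nor whether the device follows a child's blood pressure (minor)

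*Combined protocol and SAP*

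**What the plan says.** Section 17.1 lists four analyses of the paired readings: absolute differences, percentages of readings within 5 mmHg and more than 10 mmHg apart, a correlation, and a Bland-Altman analysis. The correlation sentence reads "A Pearson correlation coefficient will be calculated comparing the sBP, dBP and MAP values between the arterial cannula" and the NICCI device. It names no unit of analysis, no weight group and no handling of repeated readings. The sentence after it does so for the other method: "A Bland-Altman analysis with multiple measurements per subject will be performed to determine the bias and 95% level of agreement for the three groups".

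Section 6.2 says that simultaneous readings "will be downloaded every minute into a laptop computer for later analysis". Section 9.1 puts each child's participation at 2 to 10 hours, and section 6.1 plans 50 children in each of three weight groups.

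The endpoint in section 4.1 is stated only as a comparison: "The primary study endpoint is to compare the BP readings from the non-invasive NICCI device with those obtained from an arterial cannula". The hypothesis in section 2.1 is that "this novel non-invasive device will provide an accurate and continuous estimation of BP". Section 3.1 gives the reason for wanting a continuous device: with intermittent cuff readings, "hemodynamic events may be missed or there may be a delay in recognition of alterations in BP". Section 3.2 explains that a cuff reading, taken on the upper arm or entered by the user, sets the device's absolute level: "To calibrate the continuous pulse-contour curve with the correct absolute blood pressure values".

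**The concern.** If all one-minute pairs go into a single Pearson coefficient, two separate problems follow.

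- **It does not measure agreement.** Adding a constant to every device reading leaves r unchanged.
- **It does not isolate tracking.** It blends two associations: whether children with higher arterial pressure also have higher device readings, and whether the device moves when a given child's pressure moves. Because the level is set from a cuff, the first association could be strong even if the second were weak.

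What is at stake is interpretation. A high coefficient, published beside a hypothesis of accurate and continuous estimation, could be read as evidence of agreement or of tracking when it establishes neither. The same downloaded data can give a more informative coefficient.

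**Working it through.** The plan states no expected r, standard deviation or acceptance limit, so there is no figure of its own to reproduce.

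**Number of pairs, from the documents.** If the whole period is usable, a child gives 2 h × 60 = 120 to 10 h × 60 = 600 pairs. A weight group of 50 gives 50 × 120 = 6,000 to 50 × 600 = 30,000.

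**Offset.** A simulation assumed between- and within-child SDs of 15 and 8 mmHg and correlations of 0.9 at both levels, with 50 children and 120 pairs each. Adding 15 mmHg to the device left pooled r at 0.90. The bias went from about 0 to about 15 mmHg, and readings more than 10 mmHg apart rose from 19% to 74%.

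**Tracking.** Let b, w and e be the between-child, within-child and noise SDs, all assumed. Arterial pressure has variance b² + w². Consider these illustrative devices:

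- A, a deliberate extreme, shows each child's true mean plus noise and follows no change. Its differences have SD s = √(w² + e²).
- C follows every change but adds independent error with the same SD s.

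Then:

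- Pooled r for A = b² / √[(b² + w²)(b² + e²)]; within-child r = 0.
- Pooled r for C = √[(b² + w²) / (b² + w² + s²)]; within-child r = w / √(w² + s²).

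With b = 10, w = 8 and e = 4, s = √(64 + 16) = 8.94 mmHg:

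| | A: follows nothing | C: follows every change, with error |
|---|---|---|
| Pooled r | 100/√(164 × 116) = 0.73 | √(164/244) = 0.82 |
| Within-child r | 0 | 8/√(64 + 80) = 0.67 |
| Within-child slope on arterial pressure | 0 | 1 |
| 95% limits | ±1.96 × 8.94 = ±17.5 mmHg | ±17.5 mmHg |
| Mean absolute difference | 7.1 mmHg | 7.1 mmHg |
| Within 5 mmHg / more than 10 mmHg apart | 42% / 26% | 42% / 26% |

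The two devices have the same expected agreement summaries and differ by 0.09 in pooled r, but by 0.67 in within-child r.

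**Range.** Take b in {8, 10, 15, 20}, w in {5, 8, 10} and e = 4:

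- Pooled r for A runs from 64/√(164 × 80) = 0.56 (b = 8, w = 10) to 400/√(425 × 416) = 0.95 (b = 20, w = 5).
- C's pooled r exceeds A's by 0.004 to 0.21.
- C's within-child r is 0.62 to 0.68.

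A less favourable device gives lower values. With between-child correlation 0.9, within-child correlation 0 and equal variances in both devices, pooled r = 0.9b²/(b² + w²). That is 0.28 at b = 8, w = 12 and 0.70 at b = 15, w = 8.

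**A limit of the replacement.** Within-child r also ignores gain. Suppose a device shows each child's true mean and one quarter of every change, plus 1 mmHg noise. With w = 8, its within-child r is 2/√(4 + 1) = 0.89 but its slope is 0.25. Its differences have SD √(6² + 1²) = 6.1 mmHg. The slope is therefore needed beside the correlation.

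**The case against.** The strongest case on the other side is that little depends on this coefficient. Section 17.1 nowhere calls r a measure of agreement, and no threshold, test or decision uses it. Agreement is covered by the Bland-Altman analysis, the absolute differences and "a determination will be made of the percentage of values" within 5 mmHg and more than 10 mmHg from the arterial value. This stands, and it fixes the severity as minor.

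Four stronger readings are tempting, and the documents do not support them.

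- **That the plan pools the readings.** A reader might infer this, but 17.1 is silent. Child means or per-child coefficients are not excluded.
- **That the plan fails a tracking objective.** The objective and endpoint are to compare readings, and section 1.0 lists no secondary objectives. Tracking enters only through the word continuous in the hypothesis and through the Background.
- **That the Bland-Altman analysis is deficient because 17.1 promises only bias and limits.** A version for multiple measurements normally estimates between- and within-child variance to obtain its limits, so the gap is at most in reporting. The components would not settle tracking either: simulated values (between/within, mmHg²) were 3/77 for both A and C.
- **That the figures describe this device.** Every SD is assumed, and A is an extreme; section 3.2 describes a device that detects the pulse continuously.

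The illustration also has a limit of its own. C's error SD (8.94 mmHg) exceeds the assumed within-child SD (8 mmHg), so its readings lie further from the arterial values than each child's true mean would. Its within-child r of 0.67 could still look like useful tracking. That is a reason to read any correlation beside Bland-Altman, not a reason to prefer the pooled form.

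**Conclusion.** The point holds as a minor one, with medium confidence. Section 17.1 allows for repeated readings in one analysis and not in the one beside it. On the natural but unstated reading, the resulting r shows neither agreement nor within-child tracking. That r ignores a constant offset is exact and needs no assumption. The 0.56 to 0.95 for a device with no tracking rests on the assumed SDs and on a device that reproduces each child's mean; the 0.28 to 0.70 under the other assumptions shows how far the figure moves. The consequence is limited to one supplementary coefficient that could be over-read. The planned assessment of agreement is not undermined.

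**What to change.** In section 17.1:

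1. Calculate a repeated-measures (within-child) correlation, with child as a factor, for sBP, dBP and MAP in each weight group.
2. Report beside it the within-child slope of NICCI on arterial pressure, because the correlation ignores both offset and gain.
3. If a pooled r is kept, state that it is pooled and label it descriptive.
4. State that agreement is judged from the Bland-Altman analysis.

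As a suggestion only, report the between- and within-child variance components of the signed differences with the bias and limits. They would separate a fixed per-child offset from error within a child.

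The cost is a few sentences and a little more analysis on data already downloaded, with no new patients or measurements. The correlation will probably be lower than a pooled one. It will be low in children whose pressure barely changes, so it must be read beside the Bland-Altman result. Settling the form now also avoids choosing it after the data are seen.
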